[name]
[name]
(ph) [contact]
(fx) [contact]
[contact]

[name], B.S., Senior Research Technician

[name]
[name]
(ph) [contact] [name]
[contact]

[name], Project Assistant

[name]
[name]
(ph) [contact]
(fx) [contact]
[contact]

PARTICIPATING STUDY SITES

University of California, San Diego Medical Center in Hillcrest.
[name].
[name]
(ph) [contact]

PRÉCIS

Study Title

Alternative Treatments for Premenstrual Dysphoric Disorder

Objectives

The primary aim of this study is to examine the effects of co-administered wake therapy followed by light treatment on mood and circadian rhythms to test the hypothesis that critically timed chronotherapy improves mood by correcting phase disturbances in melatonin and sleep in women with Premenstrual Dysphoric Disorder (PMDD).

Design and Outcomes

40 women with Premenstrual Dysphoric Disorder ages 18-45 will be randomized to a cross-over design contrasting one night of Late Wake Therapy followed by 7 days of morning Bright-White Light (LWT+AM BWL) vs. one night of Early Wake Therapy followed by evening Bright-White Light (EWT+PM BWL) administered in the luteal phase of two separate menstrual cycles. Treatment will be preceded by 2 evaluation months to determine diagnosis and collect baseline mood, sleep, actigraphy and endocrine measures. To lessen the patient's burden, the 1-night EWT or LWT and the following 7-day BWL interventions will be conducted at home, given at a fixed point in each menstrual cycle, from day 1 to 7 after the mid-cycle LH surge. We anticipate that LWT+7 days of AM BWL (vs. EWT+PM BWL) will produce much greater mood benefits and larger physiological responses, than the one-time light pulses used in our earlier phase-shift studies.^{1,2}

Interventions and Duration

Using a randomized cross-over design, in the luteal phase of their menstrual cycles, PMDD women will receive either 1) one night of LWT (sleep 21:00-01:00 h, followed by wakefulness) plus 7 days of AM BWL (light-emitting diode-LED administered for 60 minutes, starting within 30 minutes of habitual wake time) or 2) EWT (wakefulness until 03:00 h, then sleep 03:00-07:00 h) plus 7 nights of PM BWL (administered 90 minutes before habitual sleep onset, for 60 minutes). Following this first intervention, patients will undergo one washout month with no intervention. The second intervention will be completed in the luteal phase of the following month and will be the treatment opposite the one previously performed. Total study duration, including evaluations and washout, will be 5 months (see Figure 1, Section 3, for detailed study flow diagram).

Sample Size and Population

In order to achieve the targeted enrollment goal of 40 completed subjects allowing for a 20% drop-out rate, 48 PMDD women ages 18-45 will be recruited to participate in the study.

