3. STUDY DESIGN

Forty PMDD subjects will be recruited. Menstrual cycle phase will be established by measuring the mid-cycle LH surge using a urinary colorimetric assay (Clearblue® colorimetric LH assay, Princeton, New Jersey). Failure to ovulate will exclude the subject from participating that month, and the study will be postponed until a following month when ovulation can be documented.

Overall Design (see Figure 1): Month 1 consists of a screening evaluation using daily mood ratings (DMR) (see Section 6: Subject Selection). In Month 2, evaluations are continued, the Structured Clinical Interview for DSM-IV (SCID)^{51, 52} and documentation of ovulation by the LH surge (approximately menstrual cycle day 14) are performed. In the Month 2 luteal phase, PMDD subjects will collect overnight urine samples for 6-SMT and reproductive hormones (RH) (estradiol, progesterone, FSH, LH, prolactin) starting 8-9 days after the LH surge (approximately menstrual cycle days 22-23). These baseline urine sample collections are timed to coincide with post-intervention measures in months 3 and 5. Starting in Month 3, after the LH surge (luteal phase), subjects will undergo a night of LWT (sleep 21:00-01:00 h, followed by wake) vs. EWT (wake until 03:00 h followed by sleep until 07:00 h) at home. We selected the specific wake and sleep times based on our previous work in

PMDD.^{36, 37} The following day, subjects will receive the light intervention for 7 consecutive days: days 1-7 after the LH surge (approximately menstrual cycle days 15-21). We will randomize subjects to 60 min of either AM bright white light (LED of 1350 lux at 20 inches) starting within 30 minutes of their habitual wake time, or PM bright white light ending 30 min before their habitual sleep onset time. After completing seven days of light exposure, subjects again will collect 30+ hours of urine samples over 2 nights (between days 8-9 after the LH surge, approximately menstrual cycle day 22-23). The following Month 4 (Washout) will be a month of no intervention to prevent any carry-over effects from the Month 3 intervention affecting measures in Month 5. Mirroring Month 3 timing, in the luteal phase of Month 5, subjects will receive the alternate wake therapy (LWT or EWT) and light exposure (AM or PM), followed by 2 overnight collections of urinary 6-SMT and RH samples. See Fig. 1, below.

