4. SELECTION AND ENROLLMENT OF PARTICIPANTS

Subjects for these experiments over 5 years will include: Forty women with premenstrual dysphoric disorder (PMDD). As only women have menstrual cycles, only women will be sought. As women generally do not develop significant premenstrual mood symptoms until late adolescence, and the menstrual cycle may become irregular during the perimenopause, only women age 18-45 years will be studied. For these reasons, children and adolescents under the age of 18 and peri- and post-menopausal women will be excluded. All ethnic groups will be represented (Caucasian, Asian, Black, Hispanic and Other). We will focus on recruiting subjects representative of the community: approximately 54% Caucasian, 30% Hispanic, 10% Asian, 5% African American and 1% Other. The UCSD Medical Center serves a clientele in which minorities are over-represented. All subjects will be adults individually competent to execute written informed consent.

Recruitment of minority subjects: We will take pains to recruit women of color and other minorities working with the Women’s Center, the Cross Cultural center, the Lesbian, Gay, Bi-Sexual and Transgender (LGBT) Resource Center, Queer People of Color (QPOC) Center and the Native American Student Alliance on the University of California campus.

	Caucasian	Hispanic	Asian	Black	Other
Female	54%	30%	10%	5%	1%

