6.2.6 Follow-up/Final Evaluation

During final visit, subjects will again perform the Hamilton, BDI, BAI and PGWI ratings (once). They will also complete the Global Assessment of Treatment Effectiveness form. Final evaluation of inclusion/exclusion criteria will be performed at this time.

After completion of the study (final visit), participants will be followed up for 1 month to monitor relapse. The Clinical Rater will telephone the patient at home during the luteal phase, around the same time in the patient's cycle as the post treatment 2 ratings were collected, to collect follow-up mood ratings (Hamilton, BDI, BAI and PGWI).

None of the subjects will be excluded from analysis, and their data will be analyzed according to the randomization scheme. Different hypotheses are included for different phases of the study. All subjects will be included in any baseline analyses regardless of their final study status. In addition to the baseline data, at least one other data point is needed in order to provide a valid estimation of a parameter for change throughout the study. The Random Regression Model was selected due to the flexibility of this method that includes all subjects with any valid data point in the analyses, as opposed to a method that is designed to examine just

the completers, such as a Repeated Measures Analysis of Variance. All subjects will be included in the analyses and we will not focus only on subjects who complete the study. Secondary analyses will be performed on data from completers. Our methods for data analyses include all subjects with any valid data points in the analyses (see Section 9.6. General Approach to Data Handling and Statistical Analyses).

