9.2 Sample Size and Randomization

For our primary outcome measures of mood, based on our earlier data reflecting

seven days of light exposure alone² (i.e., without the ‘priming’ effect of wake therapy), we predict the following changes in mood in PMDD subjects (N = 40) after Late Wake Therapy plus AM Light vs. Early Wake Therapy plus PM Light: A significantly greater improvement (decrease in raw score) will be detected at the p = .05 level with (a) 71% power in Hamilton Rating Scale for Depression (HRSD) Score (Mean difference 3.15±9; effect size = .324); (b) > 99% power in atypical score (Mean difference 4.45±5; effect size = .78); (c) > 99 % power in Structured Interview Guide for the Hamilton Depression Rating Scale, Seasonal Affective Disorders (SIGH-SAD) Items (Mean difference 7.0±11; effect size = .627); (d) 86% power in Beck Depression Inventory (BDI) score (Mean difference 6.30±15; effect size = .378).

For the recovery criterion of $\geq 50\%$ decrease from baseline (Chi Square analyses): (a) 97% power for HRSD score (difference in proportions: .44); (b) 70% power for atypical score (difference in proportions: .30); (c) 86% for SIGH-SAD score (difference in proportions: .325); and (d) 93% power for BDI score (difference in proportions: .40). For the remission criterion of reduction to a score of ≤ 8 (Chi Square analyses): (a) 89% power for the SIGH-SAD score; (b) 44% power for the BDI score. All tests are two-tailed.

We also performed power analyses for the primary hypotheses, incorporating the longitudinal nature of the design for the proposed Random Regression model (also known as Multilevel Models, or Growth Curve Models). Procedures describes by Hedeker et al.⁶⁹ for Random Regression Models, with the above data, was used for the proposed study to estimated needed sample size. We assume a Type-I error level (alpha-level) of 0.05, drop-out rate of 10% to 15% and an autoregressive covariance structure, with correlation between sequential assessments set at 0.45 (based on our previous data). We are confident based on our results from these two separate approaches that the proposed study will have minimum power of 80% to yield a statistically significant result for a medium effect size. Here, medium effect size is defined as a treatment difference increasing linearly from 0 at baseline to .5 SD units at the last time point. Type 1 error will be controlled by correcting the p-value per domain.

Treatment Assignment Procedures

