Specifically, data for hypothesis 1.A. will be analyzed using a Random Regression Model (RRM), a generalized linear model described by Gibbons et al.,⁷⁴ Hedeker et al.⁶⁹ and Laird.⁷⁵ The random effects method has several advantages over more traditional analytic approaches such as a change score, end-point or repeated measures analysis of variance. This method allows the inclusion of subjects with missing data or those who were terminated early in the study, without relying on data imputation procedures. This method provides an estimate of the individual variability around the population trend, the variability of the individual intercepts (baseline values) and slopes (changes across time), and the correlation between them. A fully saturated treatment by time model will be utilized for inference. Co-variance structure will be chosen based on Akaike's Information Criterion (AIC). Random treatment effects also will be evaluated for importance based on the model AIC. This plan allows for any group level effects to be incorporated into the model. Denominator degrees of freedom will be calculated using the Kenward-Roger small sample correction. All subjects will be included in the analyses, and we will not focus only on subjects who complete the study. Our methods for data analyses include all subjects with any valid data points in the analyses. Secondary analyses will be performed on data from completers. Type 1 error will be controlled by correcting the p-value per domain. For hypothesis 1.B, an individual's slope for each of the dependent variables listed above will be calculated and will be used for correlational analysis using the Pearson method. In addition, we will examine the number of responders. The operational definition of the criteria for

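### The recruitment target of 48 does not give 40 completers at the stated 20% drop-out: it gives about 38, and 40 would need 50 recruits

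*Combined protocol and SAP*

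**What the plan says.** The recruitment calculation is a single sentence in the Precis, under Sample Size and Population: "In order to achieve the targeted enrollment goal of 40 completed subjects allowing for a 20% drop-out rate, 48 PMDD women" aged 18–45 will be recruited.

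Section 9.2 uses 40 for its first set of powers (mean mood scores, response and remission). For the separate random regression power calculation it assumes a "drop-out rate of 10% to 15% and an autoregressive covariance structure". Nothing in the plan relates that rate to the 20% in the Precis.

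Elsewhere 40 appears without being identified as the number of completers. In the Precis, under Design and Outcomes, "40 women with Premenstrual Dysphoric Disorder ages 18-45 will be randomized to a cross-over design". In section 3, "Forty PMDD subjects will be recruited". Sections 4 and 9.3 also give forty, as the women to be included and to be selected.

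On the use of incomplete data, section 9.6 says: "Our methods for data analyses include all subjects with any valid data points in the analyses". Section 6.2.6 says the same. Both make the completer analysis secondary.

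**The concern.** A drop-out rate applies to the women who enter. To finish with a given number after losing a fraction *d*, the target is divided by 1 − *d*. The Precis appears to have multiplied the target by 1 + *d* instead, which always gives too small a number.

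At stake is whether the stated recruitment delivers the N at which section 9.2 quotes its powers. Some of those have little slack by the plan's own figures: 71% for HRSD, 70% for response on the atypical score and 44% for remission on the BDI. This is also the only recruitment number in the plan that allows for drop-out, so it is what a reader will use to judge whether the trial met its target.

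**Working it through.** **Inputs.** Target 40 completers, drop-out 20% and 48 recruited (Precis, Sample Size and Population). N = 40, two-sided α = 0.05, effect sizes, drop-out 10–15% and correlation 0.45 between sequential assessments (section 9.2).

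**1. Reproducing the plan's figure.** 40 × (1 + 0.20) = 48 exactly.

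**2. The correct calculation.**
- Expected completers from 48: 48 × (1 − 0.20) = 38.4, a shortfall of 1.6.
- Recruits needed for 40: 40/(1 − 0.20) = 50, which is 2 more than planned.
- Largest drop-out at which 48 still gives 40: (48 − 40)/48 = 16.7%.
- At section 9.2's rates: 48 × 0.85 = 40.8 and 48 × 0.90 = 43.2.

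**3. Chance of at least 40 completers**, assuming women drop out independently (binomial):

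| Recruited | Drop-out | Expected completers | P(at least 40) |
|---|---|---|---|
| 48 | 20% | 38.4 | 36% |
| 48 | 16.7% | 40.0 | 59% |
| 48 | 15% | 40.8 | 71% |
| 48 | 10% | 43.2 | 95% |
| 50 | 20% | 40.0 | 58% |

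**4. Effect on power if only completers count.** Section 9.2 does not name its test for the mean scores, so a two-sided paired t-test is used as an illustration (noncentrality *d*√N, N − 1 degrees of freedom). Only the differences across a row matter here; the absolute levels are not offered as a check of the plan's stated powers. HRSD and BDI are shown both at the quoted effect size and at the ratio of the quoted mean difference to the figure after the ±.

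| Measure | *d* | N = 40 | N = 38.4 | N = 38 |
|---|---|---|---|---|
| HRSD | 0.324 | 51.5% | 49.8% | 49.4% |
| HRSD | 3.15/9 = 0.35 | 57.9% | 56.1% | 55.6% |
| BDI | 0.378 | 64.5% | 62.6% | 62.2% |
| BDI | 6.30/15 = 0.42 | 73.6% | 71.7% | 71.3% |
| SIGH-SAD | 0.627 | 97.2% | 96.6% | 96.4% |

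From 40 to 38 the loss is 2.1–2.3 points for HRSD and BDI and less than 1 point for SIGH-SAD. At 38.4 it is 1.7–1.9 points for HRSD and BDI.

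**5. Effect when partial data are kept.** Take a simplified two-period crossover with mean, period and treatment effects, balanced sequences, equal variances and between-period correlation ρ. With treatment coded ±½, a completer contributes information 1/[2(1 − ρ)] on the treatment difference, and a woman with period 1 only contributes 1/4. One period-1-only woman is therefore worth (1 − ρ)/2 of a completer, and the total in completer-equivalents is 38.4 + M(1 − ρ)/2, where M is the number with period 1 only.

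Expected drop-outs are 48 × 0.20 = 9.6. If half give period-1 data, M = 4.8:
- ρ = 0.30: 38.4 + 4.8 × 0.35 = 40.1
- ρ = 0.45: 38.4 + 4.8 × 0.275 = 39.7
- ρ = 0.60: 38.4 + 4.8 × 0.20 = 39.4
- ρ = 0.80: 38.4 + 4.8 × 0.10 = 38.9

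If no drop-out gives period-1 data, the total stays at 38.4 for any ρ. If all 9.6 do, at ρ = 0.45 it is 38.4 + 9.6 × 0.275 = 41.0. The plan gives 0.45 for sequential assessments; using it between periods is an assumption, as is the share of drop-outs with period-1 data.

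**The case against.** The best defence is that 48 may be right and the 20% label wrong. Eight extra women are exactly 20% of 40, so the sentence is coherent if the 20% is an over-recruitment allowance on the target. And 48 fits the upper end of section 9.2's range: 40/0.85 = 47.1, which rounds up to 48. The plan also does not say from what point drop-out is counted.

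This stands in part. The wrong item could be the 20% rather than the 48, and the sponsor is the one to say which. But the sentence calls its 20% a drop-out rate and sets its target in completed subjects, and on that wording the figures disagree. If eight spare women were meant, the drop-out they cover is 16.7%, and the text should say so. The 10–15% may serve a different purpose from the recruitment allowance, so the difference between the two rates is not counted here as an error.

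The second defence is consequence. The gap is two recruits, section 9.2 does not say that its N = 40 means completers, and the main model keeps women with partial data. In the favourable case where every drop-out gives period-1 data, the information is worth 41.0 completers, more than 40. This stands as a reason to call the point minor. It does not make the sentence true, because that target is stated in completers.

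**Conclusion.** The concern holds as a minor arithmetic error. As written, 48 recruits at 20% drop-out give 38.4 expected completers, not 40, and under independent drop-out the trial is more likely than not to miss 40 (1 − 0.36 = 64%). The consequence is small: about 2 points of power or less if only completers count, on a test the plan does not itself specify, and less in the main model unless none of the drop-outs contributes period-1 data. The arithmetic needs only the three numbers in the sentence and the usual meaning of a drop-out rate. It should be corrected because it is a stated sample-size figure that the stated design does not deliver, and correction costs almost nothing.

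**What to change.** Correct the Precis sentence in one of three ways:

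- **(a)** Keep 48 and 20%, and state about 38 expected completers. Restate the N = 40 powers in section 9.2 at 38 by the sponsor's own method; a drop of about 2 points or less is to be expected. No added patients.
- **(b)** Keep 48 and 40, and state that this holds if drop-out is no more than 16.7%. This is compatible with the 10–15% in section 9.2, but the sponsor must be able to support a rate below the 20% now stated. No added patients.
- **(c)** Keep 20% and 40, and recruit 50. This adds two women, at the sponsor's choice.

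Two wording changes should go with it. Add one sentence in section 9.2 saying how the 20% recruitment allowance relates to the 10–15% in the power calculation, and from what point drop-out is counted. Where 40 appears in the Precis (Design and Outcomes) and in sections 3, 4 and 9.3, label it as the completer target, following the Precis's own definition; if the sponsor means something else in any of those places, say what.

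The total cost is one corrected sentence, one linking sentence and four labels, plus the restated powers under (a), the supporting evidence under (b) or two recruits under (c).

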1. STUDY OBJECTIVES

1.1 Primary Objective

We will assess the effects of the proposed study interventions on mood, urinary melatonin, sleep and activity to test the following specific hypothesis:

For PMDD patients in the symptomatic luteal phase, LWT+AM BWL, compared

with EWT+PM BWL, will: A) Improve mood on rating scales; B) Phase-advance urinary melatonin timing measures in relation to clock time and sleep measures; C) The magnitude of the mood change will correlate with the magnitude of the phase-advance in melatonin.

1.2 Secondary Objectives

We will assess the effects of the proposed interventions on reproductive hormones. In addition, we will test the effects of expectation, morningness/eveningness and seasonality on primary outcome measures of mood, melatonin and sleep. We will evaluate subjective assessments of side effects to treatment and effectiveness.

2. BACKGROUND AND RATIONALE

2.1 Background on Condition, Disease, or Other Primary Study Focus

PMDD is a devastating illness, causing extensive personal suffering, disruption in interpersonal and family relationships and occupational impairment. It can progress to major depressive disorder (MDD)^{3, 4} and exacerbate the course of bipolar illness,^{5, 6} pregnancy, postpartum and menopausal depression.⁷ The incidence of women with severe premenstrual mood symptoms who meet criteria for a mental disorder has been estimated at 5-8%.⁸⁻¹⁰ In addition, 20% to 80% of women report some mood, cognitive, and behavioral disturbances associated with their menstrual cycle.³ Current treatments of PMDD are marginal (< 60% response).¹¹ Many women do not want to use, or cannot tolerate, chronic antidepressant medications for a periodic illness. Consequently, enhanced treatment approaches are needed to improve health outcomes.¹² The NIH Office of Research for Women's Health (Planning the Women's Health Agenda for the 21st Century, November, 1997, Bethesda, MD) targeted PMDD as an area for increased research on women's mental health, now mandated by Congress. PMDD was a DSM-IV⁸ criterion set designated for further study in the appendix,¹³ but will be incorporated into the DSM-5.¹⁴

Women are underrepresented in studies of sleep and circadian rhythms.^{15, 16} A translational comprehensive approach to studying the chronobiological abnormalities in PMDD can serve to develop new, alternative non-pharmacological treatment strategies of sleep and wake therapies. The key to establishing synchronized rhythms associated with healthy mood states is intervention at critical clock times. To achieve this objective, a better understanding of the optimal timing of wake and light interventions is needed. Elucidating the factors contributing to PMDD also will enhance our understanding and treatment of other female-specific mood disorders that involve alteration of reproductive hormones (e.g., pregnancy, postpartum and menopausal depression). Another positive outcome may be optimization of sleep and wake therapies applied to other types of depression with chronobiological disturbances, given the similarity of their phenomenology and possible pathogenic mechanisms.

